12. STUDY POPULATION

12.1 SELECTION OF STUDY POPULATION

Subjects will be recruited using a register of healthy volunteers at CTC and from advertising in media. The total sample size and the sample size per treatment group were determined as outlined in Section 18.2.

Approximately 243 subjects are planned to be screened in order to identify 162 subjects eligible for randomisation.

12.2 INFORMED CONSENT

It is the responsibility of the Investigator, or any authorised designee, to give each potential subject adequate verbal and written information about the nature of the study, its purpose, expected duration, the benefits and risks involved in study participation before any study specific assessments are performed.

All subjects will be given the opportunity to ask questions and will be informed of their right to withdraw from the study without prejudice.

Each subject should be informed in writing that the data from the study will be stored and analysed, maintaining confidentiality in accordance with local data protection laws.

The subjects will also be informed about the possibility of audits by authorised representatives of the company and/or concerned competent authorities in which case a review of those parts of the medical and laboratory records relevant to the study may be required.

After this explanation and before entering the study, the ICF must be signed and personally dated by the subject and by the person who conducted the informed consent discussion. A copy of the subject information sheet, including the signed ICF, will be provided to the subject.

The date of informed consent must be recorded in the source documentation and in the eCRF. The subject information sheet and the signed ICF should be filed by the Investigator for possible future audits and/or inspections.

12.3 SUBJECT SCREENING AND SUBJECT IDENTIFICATION LOGS

Investigators must keep a record of all subjects that were considered for enrolment even if they were not subsequently enrolled. This information is necessary to verify that the subject population was selected without bias. The reasons for non-eligibility are to be defined in terms of one or more of the eligibility criteria.

A screening number will be allocated to each subject in connection to the informed consent process at screening (Visit 1). The screening number is generated automatically by the eCRF. The screening number allow for identification of subjects irrespective of their possible eligibility for the main study. Randomised subjects will be assigned a randomisation number.

12.4 INCLUSION CRITERIA

For inclusion in this study, subjects must fulfil all of the following criteria:

1. Signed informed consent prior to any study related procedures.
2. Male or female 18-39 years of age (both inclusive) at the time of the first treatment with study drug.
3. Subjects who the Investigator believes will comply with the requirements of the protocol.
4. BMI: 18.0 and 30.0 kg/m² (inclusive).

5. Judged by the Investigator to have no serious illness based on medical history, physical examination, ECG, vital signs and blood and urine assessments at screening.
6. From the signing of the informed consent until 2 months after the last vaccination (Visit 3 for group 1 to 4 and Visit 2 for group 5 and 6) female subjects have to use contraceptive methods with a failure rate of < 1% to prevent pregnancy (combined [oestrogen and progestogen containing] hormonal contraception associated with inhibition of ovulation [oral, intravaginal, transdermal], progestogen- only hormonal contraception associated with inhibition of ovulation [oral, injectable, implantable], intrauterine device [IUD], intrauterine hormone-releasing system [IUS], bilateral tubal occlusion, sexual abstinence). Any male partner should be willing to use condom or should be vasectomized.

12.5 EXCLUSION CRITERIA

Subjects must not be included in this study if any of the following exclusion criteria is fulfilled:

1. Diagnosis of laboratory-confirmed influenza in the 2015/2016 season.
2. Use of any investigational drug product within 3 months before screening or planned use during the study period, including the safety follow-up.
3. Administration of an influenza vaccine during the 6 months before screening.
4. Previously received another vaccine within 28 days before administration of the study vaccine, or is scheduled to receive another vaccine during the study period, excluding the safety follow-up.
5. Any contra-indication to [REDACTED]
6. Any contra-indication to [REDACTED]
7. History of any anaphylactic reaction and/or serious allergic reaction following a vaccination, a proven hypersensitivity to any component of the study vaccine (e.g., to eggs or egg product as well as ovalbumin, chicken protein, chicken feathers, influenza viral protein, kanamycin, gentamycin and neomycin sulphate).
8. Diagnosis of asthma with poor disease control as assessed by the Investigator.
9. Potent immunosuppressive therapy including cytostatics, antibodies, drugs acting on immunophilins, interferons and other drugs used to prevent rejection of organ transplants, within 6 months before screening.
10. Use of any parenteral or oral corticosteroids within 30 days prior to screening. Inhaled steroids are allowed.
11. Any confirmed or suspected immunosuppressive or immunodeficient condition, based on medical history and physical examination.
12. Any progressive or severe neurologic disorder, seizure disorder or Guillain-Barré syndrome.
13. History of Guillain-Barré syndrome within 6 weeks of receipt of prior inactivated influenza virus vaccine.
14. Received blood, blood products and/or plasma derivatives or any administration of immunoglobulin preparation within the three months prior to Visit 2, or planned during the study.
15. Participation in blood donation within 3 months or plasma donation within 1 month prior to Visit 2.
16. History of substance or alcohol abuse within the past 2 years.
17. History or any illness/condition that, in the opinion of the Investigator, might interfere with the results of the study or pose additional risk to the subjects due to participation in the study.

18. Any positive result on screening for serum hepatitis B surface antigen, hepatitis C antibody and HIV.
19. Pregnant or lactating female or intent to become pregnant during the clinic phase (up until and including Visit 4 for group 1 to 4 and Visit 3 for group 5 and 6) and for 2 months after the last vaccination.
20. History of Bell's palsy.
21. Ongoing regular use of intranasal sprays including corticosteroids and decongestants.
22. Ongoing cough, sinusitis, allergic rhinitis, nasal polyps or obstruction, including septum deviation significant enough to prevent bilateral administration of study vaccine.
23. Known bleeding diathesis, or any condition that may be associated with a prolonged bleeding time.
24. Subjects that are prone to nosebleed.

12.6 CONTINUED ELIGIBILITY CRITERIA (TO BE CHECKED BEFORE FIRST AND SECOND DOSE)

At Visit 2, subjects **must not** be randomised if they comply with any of the following criteria:

1. Temperature $\geq 38.0^{\circ}\text{C}$ and/or any acute illness within 3 days prior to study treatment.
2. Ongoing cough, sinusitis, allergic rhinitis, nasal polyps or obstruction, including septum deviation significant enough to prevent bilateral administration of study vaccine.
3. Blocked nose (subject must be able to breath in an out of each nostril when blocking the other nostril by pressing a finger against the wing of his/her nose).
4. Use of nasally administered prescription or nasally over-the counter (OTC) medications within 2 days prior to treatment.
5. Use of other investigational product since screening.
6. Participation in blood donation since screening (plasma donation within 1 month of Visit 2) or planned during the study.
7. Planned influenza vaccination during the study period including the safety follow-up period.
8. Laboratory-confirmed influenza since last visit.

Subjects who fulfil any of the continued eligibility criteria may be rescheduled for a second evaluation of continued eligibility at the discretion of the Investigator.

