12.8.3 Procedure for withdrawal

The date and reason for withdrawal of a subject or the premature termination of the study must be documented in the eCRF.

After withdrawal of a subject, all AEs or complications should be followed for as long as the Investigator considers it necessary.

Subjects who have received at least one dose of study drug should as far as possible be followed for safety according to the protocol. Blood and nasal sampling for immunology parameters will not be performed.

Subjects who have received one dose of study drug and are diagnosed with laboratory-confirmed influenza prior to the second dose should not receive a second vaccination but should, as far as possible, be followed for safety according to the protocol. Blood and nasal sampling for immunology parameters will not be performed.

Subjects who withdraw before receiving any IMP should not participate in any further study related procedures.

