12.8.4 Replacement of withdrawn subjects

Randomised subjects will not be replaced.

Subjects who develop suspected influenza during the study period should be tested using a diagnostic test at the discretion of the Investigator (Section 15.10). If influenza is confirmed no further treatment with study drug should be given. Safety should as far as possible be followed according to the protocol excluding further sampling for immune parameters. Subjects diagnosed with influenza before receiving any study drug should not participate in any further study related procedures.

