- Recording of vital signs at 30 minutes and approximately 120 minutes post study drug administration (before the subject leaves the clinic).
- AE collection.
- Diary instructions for daily AE recording during 10 days starting in the evening the day after treatment.

14.1.3 Visit 3

The activities and assessments to be performed at Visit 3 are outlined below. A re-assessment of eligibility will be made prior to dosing, see Section 12.6. For details on the timing of each assessment, refer to Table 1, Table 2 and Table 3.

14.1.3.1 Visit 3 group 1 to 4

The following activities and assessments will be performed **pre-dose**:

- Pregnancy test (females only, urine dipstick).
- Review of diary since the previous visit.
- AE collection.
- Recording of concomitant medication.
- Recording of vital signs (heart rate, blood pressure and body temperature).
- Nasal swab for nasal IgA sampling (at least 60 minutes before assessment of the pre-dose assessment of local tolerability).
- Blood sampling for immunology analyses.
- Inspection of nasal cavities and recording of local tolerability parameters.

Nasal **study drug administration** will be performed as summarized in Section 13.5.1.

The following activities and assessments will be performed **post-dose**:

- Recording of local tolerability parameters at 15 and 120 minutes post study drug administration.
- Recording of vital signs at 30 minutes and approximately 120 minutes post study drug administration.
- AE collection.
- Diary instructions for daily AE recording during 10 days starting in the evening the day after treatment.

14.1.3.2 Visit 3 group 5 and 6

The following activities and assessments will be performed:

- Review of diary since the previous visit.

- AE collection.
- Recording of concomitant medication.
- Recording of vital signs (heart rate and blood pressure).
- 12-lead ECG.
- Physical examination.
- Urine sampling of urinalysis parameters.
- Blood sampling for assessment of haematology and clinical chemistry parameters. Fasting is not required.
- Nasal swab for nasal IgA analysis.
- Blood sampling for immunology analyses.

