18.4.2 Per-protocol Analysis Set

The per-protocol analysis set (PPAS) is a subset of the FAS and consists of all subjects without any major protocol deviations, i.e. a set of subjects that participated in the study as intended.

Analysis based on the PPAS will be used to assess the robustness of the results from the FAS analyses. Subjects will be analysed according to treatment which they received.

Subjects diagnosed with influenza after start of treatment will not be included in the PPAS.

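### Section 12.6 lets a subject with confirmed influenza be rescheduled for re-evaluation, which contradicts 12.8.3 and 12.8.4; the PPAS influenza rule does not reach a case confirmed before dose 1

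*Combined protocol and SAP*

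**What the plan says.** Section 12.6 lists eight conditions that keep a subject from being randomised at Visit 2. The eighth is "Laboratory-confirmed influenza since last visit". The section then adds: "Subjects who fulfil any of the continued eligibility criteria may be rescheduled for a second evaluation of continued eligibility", at the investigator's discretion. No criterion is exempted. The heading extends the checks to both doses, and 14.1.3 applies them at Visit 3: "A re-assessment of eligibility will be made prior to dosing, see Section 12.6".

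Section 12.8 deals with the same subjects differently.

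- Before dose 1, 12.8.4 says: "Subjects diagnosed with influenza before receiving any study drug should not participate in any further study related procedures".
- Between doses, 12.8.3 says that subjects who have had one dose and "are diagnosed with laboratory-confirmed influenza prior to the second dose should not receive a second vaccination". Safety follow-up continues, but blood and nasal sampling for immunology stops. Section 12.8.4 likewise ends study drug and immune sampling once influenza is confirmed.

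On analysis sets, 18.4.2 says: "Subjects diagnosed with influenza after start of treatment will not be included in the PPAS". It also removes subjects with major protocol deviations, a term it does not define. Section 18.4 leaves classification to the first clean file meeting.

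**The concern.** The same subject can receive opposite instructions on re-evaluation, dosing and sampling, depending on which section a site reads. There are two sites, and 12.6 leaves rescheduling to the investigator's discretion. This concerns the subject's care as well as the data, so the passages must be reconciled.

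The analysis is affected too. A subject vaccinated soon after natural infection may show an antibody rise that the product did not cause. In any arm, including the saline arm that serves as the control for background antibody, that rise would be read as response to treatment.

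**Working it through.** There is no design figure to reproduce: 18.2 states that sample size does not rest on a power calculation. The check sets the passages side by side for two subjects.

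1. **Influenza confirmed between Visit 1 and the planned Day 0.** Exclusion criterion 1 (12.5) covers only the 2015/2016 season, so it does not catch this subject. Under 12.6 the subject meets criterion 8 and may be brought back for a second evaluation. Under 12.8.4 the subject takes part in nothing further. A second eligibility evaluation is itself a study procedure, so the two sections conflict whatever its outcome. The influenza rule in 12.8.3 does not apply, because it presupposes one dose.

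2. **Influenza confirmed on, say, Day 15, Groups 1-4.** Section 13.5.1 allows 3 to 4 weeks between doses, which leaves 28 − 21 = 7 days for rescheduling. Under 12.6 the subject meets criterion 8 on Day 21 and may be re-evaluated by Day 28. Under 12.8.3 and 12.8.4 there is no second dose and no further immunology sampling. Groups 5 and 6 have one dose, so this case cannot arise there.

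3. **Outcome of the second evaluation.** Criteria 5 and 6 of 12.6 are dated from screening. Criterion 8 is dated from the last visit, which is not defined for a repeat attendance.
   - If the failed attendance is the last visit, the influenza precedes it, criterion 8 is no longer met, and the subject could be dosed.
   - If the last visit is the previous numbered visit (Visit 1, or Visit 2 for dose 2), criterion 8 is still met and the subject fails again.

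4. **FAS (18.4.1: one dose plus a post-randomisation efficacy assessment).**
   - Subject 1: under 12.8.4, never randomised and outside the FAS. Under 12.6, if passed, then dosed and sampled at Day 21, and inside it.
   - Subject 2: under 12.8.3 and 12.8.4, no sample after Day 0 and outside the FAS. Under 12.6, if the Visit 3 pre-dose samples are taken, inside it.
   - This assumes that the Visit 2 blood sample, taken after randomisation but before dosing (14.1.2), does not count as the qualifying assessment. If it does, subject 2 is in the FAS either way but has no post-treatment value under 12.8.

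5. **PPAS (18.4.2).** Subject 2 is removed by the influenza sentence. Subject 1 is not, because the diagnosis precedes treatment. Removal would require the dosing to be classed as a major deviation. It conflicts with 12.8.4 but appears to be permitted by 12.6, so the clean file meeting could decide either way.

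6. **Effect on the endpoints for subject 1.**
   - Nasal IgA: the baseline swab is taken at screening (14.1.1), up to 42 days before Day 0. The infection falls between baseline and the first post-treatment swab, so its IgA rise could count as response.
   - HI and VN: baseline is drawn pre-dose at Visit 2 (14.1.2), after the infection. If HI has already reached 40, for illustration, the fourfold rule requires 4 × 40 = 160, against 40 from a baseline below 10. If titres are still rising, part of the later rise is credited to the product. The direction of bias is uncertain.

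7. **Scale.** Group sizes are 36 and 18 (3 × 36 + 3 × 18 = 162). With full groups, one subject moves a percentage such as seroconversion by at most 1/36 = 2.8 points in Groups 1-3 or 1/18 = 5.6 points in Groups 4-6. The documents give no expected number of cases.

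**The case against.** The best defence is that 12.6 grants only a second evaluation, not a dose, and that the specific rules in 12.8.3 and 12.8.4 limit the general one. For dose 2 this has force: an investigator who reads both sections would probably withhold the dose. It does not resolve the case before dose 1, where 12.8.4 rules out the evaluation itself. Nor does 12.6 refer to 12.8 or exempt criterion 8.

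The expected impact is also limited. Section 9.6 plans treatment before the expected 2016/2017 outbreak. The primary endpoints are descriptive safety endpoints, and 18.5.3.1 calls the immunogenicity comparisons exploratory. All of this stands and limits the size of the point.

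Four stronger inferences are tempting, and the documents do not support them.

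- A reader might infer that a rescheduled subject will pass. That depends on the undefined last visit; under the numbered-visit reading the subject fails again.
- A reader might infer that a case before dose 1 will stay in the PPAS. Major deviations are also removed, 18.1 provides for a blinded review of evaluability, and a SAP is to be finalised before code-breaking. Only *could stay* is supported.
- A reader might infer that HI and VN responses would be inflated. Their baseline follows the infection, and the ANCOVA adjusts for baseline.
- A reader might extend the point to criterion 5 (another investigational product) because 12.8.1 lists this as a reason for discontinuation. Criterion 5 is fixed at screening, so a repeat visit cannot reset it, and 12.8.1 is discretionary.

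**Conclusion.** The contradiction stands on the text: 12.6 against 12.8.4 before dose 1, and 12.6 against 12.8.3 and 12.8.4 between doses in Groups 1-4. Whether a rescheduled subject is then dosed depends on how a site reads the last visit. FAS membership follows from which section is applied, subject to the assumption about the Visit 2 sample. PPAS membership of a case before dose 1 is left open rather than wrongly fixed.

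The consequence for the analysis is clearest for nasal IgA and of uncertain direction for HI and VN. It amounts to at most 2.8 or 5.6 percentage points per retained case on a seroconversion percentage, with an unknown and possibly small number of cases. The reason to act is that the sections give conflicting instructions on dosing and sampling a participant, and correcting the wording costs little.

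**What to change.** Four wording changes:

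- Reconcile the rescheduling sentence in 12.6 with 12.8.3 and 12.8.4, so that one rule governs confirmed influenza before dose 1 and one governs it between doses. Which clinical rule stands is for the sponsor to decide.
- State which of the eight criteria in 12.6 the rescheduling sentence covers.
- Define the last visit in criterion 8 for a repeat evaluation.
- Extend the influenza exclusion in 18.4.2 to influenza confirmed from screening onward, and fix this before code-breaking.

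The cost is protocol wording in 12.6, 12.8 and 18.4.2. No new data are needed. At most a few subjects leave the PPAS, and comparing FAS with PPAS then serves as the robustness check that 18.4.2 intends.

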12.7 RESTRICTIONS

12.7.1 General restrictions

The following restrictions must be respected by the subjects during the participation in the study:

- Contraception requirements as detailed in Inclusion criterion #6.
- Subjects must not donate blood or plasma during the study until 3 months after Visit 4 (group 1 to 4) and Visit 3 (group 5 and 6).
- Subjects must not use any other investigational drug product during the study period including the safety follow-up period.

Restrictions related to concomitant therapy are described in Section 12.7.2.

12.7.2 Prior and concomitant therapy

From screening until the last visit to the clinic, subjects should abstain from intake of oral corticosteroids and potent immune modulating drugs as indicated in exclusion criteria #9 and #10.

Use of nasally administered prescription or nasal OTC medications within 2 days prior to each treatment are not allowed.

Influenza vaccination is not allowed during the study period including the safety follow-up period. Vaccination with other licenced vaccines are allowed after the last visit to the clinic.

12.8 WITHDRAWAL OF A SUBJECT, DISCONTINUATION OF TREATMENT AND STUDY TERMINATION

12.8.1 Subject withdrawal

Subjects have the right to withdraw consent at any time, for whatever reason, without prejudice. Subjects who withdraw will be asked about the reason(s) for withdrawal, and the presence of any AEs.

If a subject does not return for a scheduled visit, every effort should be made to contact the subject for follow-up assessments.

Subjects may be discontinued from the study at any time at the discretion of the Investigator. Specific reasons for discontinuing a subject from further assessments are:

- Withdrawal of informed consent.
- Subject lost to follow-up (*i.e.* drop-outs).
- Death.
- Any violation of, or deviation from, study protocol procedures which, in the judgment of the responsible physician, could adversely affect the subjects or the integrity of the study.
- The Investigator considers that it is not in the interest of the subject to continue.
- Any AE, clinically significant laboratory abnormality, inter-current illness or significant worsening of inter-current illness which, in the opinion of the Investigator, is posing a risk for the subject.
- Occurrence of an exclusion criterion which is clinically relevant and affects the subject's safety, if discontinuation is considered necessary by the Investigator and/or Sponsor.
- Taking another investigational drug treatment during the subject's involvement in the study *i.e.*, from screening to the last follow-up telephone call.

12.8.2 Study termination

Eurocine Vaccines AB, in collaboration with the Investigator and after detailed consultation with PCG, reserves the right to terminate the study prematurely for the event of an outbreak of pandemic influenza early during the study conduct, for scientific or administrative reasons or for any other valid and/or ethical reason. If the study is prematurely terminated, the Investigator should promptly inform the subjects and take necessary steps to finalise their engagement in the study, preferably according to the scheme for the final safety assessments to be conducted at Visit 4 (group 1 to 4) and Visit 3 (group 5 to 6), respectively. All relevant study material must then be collected and accountability completed.

If the study is prematurely terminated by the Sponsor, subjects who have received at least one dose of investigational medicinal product (IMP) should as far as possible be followed for safety according to the protocol, excluding sampling for immune parameters.

